Power analysis and estimate of sample size for Experiment 1 [name] (our biostatistician consultant) has performed power analysis based on our pilot study and historical data from the literature. A two-way repeated measures ANOVA was used to determine whether any change in VAS score was due to the interaction between INTERVENTION and TIME (i.e. whether one of two interventions is more effective at reducing VAS scores). A power analysis using the G*power computer program (Faul et al. 2007) indicated that a sample of 12 people would be needed to detect a large effect size (> 0.8) with 85% power using a repeated measures two-way ANOVA with alpha at .05, a sample of 14 people would be needed for 90% power. To account for possible subject withdrawal (10%), we plan to recruit 16 subjects. Also to reduce the experimental bias and the order effect, the order of the interventions will be randomized.

Pilot data and sample size for Experiment 2 (Aim 2)

In Experiment 2, the same BreESTim protocol will be used, but at two different doses (120 stimuli vs. 240 stimuli). We have tested the protocol in 4 patients with phantom limb pain after BKA (Figure 5). On average, BreESTim120 and BreESTim240 had similar analgesic effects. VAS decreased from 6.4 to 3.5 after BreESTim120, and from 5.9 to 3.5 after BreESTim300. However, the analgesic effect lasted longer after BreESTim240 (26.1 hours) than after BreESTim120 (14.5 hours). Similar to Experiment 1, these data are from IRB approved study MS-20-1032

analgesic effects were paralleled with similar degrees of change in EPT without changes in other thresholds.

[figure not shown]

[figure not shown]
Figure 5 BreESTim has a dose-response effect on the duration, not the degree of analgesic effects on phantom limb pain.

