Power analysis and estimate of sample size for Experiment 3 [name] (our biostatistician consultant) has performed power analysis based on our pilot study and historical data from the literature. Using nQuery Advisor®, we applied the t-test (ANOVA) for difference of VAS in 2 x 2 crossover design with a 0.05 two-sided significance level. To achieve 80% power of detecting a difference in VAS of 3.0 (the difference between the mean of group BreESTim, $\mu_1=4.0$ and the mean of EStim group, $\mu_2=2.0$) assuming that the Crossover ANOVA \sqrt{MSE} is 3.4 (the Standard deviation of differences, σ_d , is 4.8), the sample size is 24. Assuming an expected dropout rate of 20% given the long-term intervention, we proposed to recruit 30 patients in total for Experiment 3.

D. The data collection and measurement techniques are appropriate and effective

- **Experimental Design**

The overall research design is a within-group, randomized controlled study to compare analgesic effects between EStim and BreESTim (single-session in Exp 1, long-term intervention in Exp 3), between BreESTim120 and BreESTim240 (Exp2). We prefer this within-group comparison because 1) pain, by nature, is a subjective perception, it is difficult to control (physical, social, psychological) multi-factors between two groups; 2) It will be fair that all subjects receive the innovative intervention, which is superior to regular electrical stimulation according to our pilot data; 3) according to our recent BreESTim study in patients with spinal cord injury, the duration of analgesic effect was 15 hours after one-session of BreESTim treatment. An interval of one week for washout should be sufficient for Exp 1 & 2. The washout interval will be 2 weeks for Exp 3. It is our experience with subjects with spinal cord injury that an interval of 7 days is sufficient for subjects to return to their baseline after BreESTim treatment. (Li et al. 2016; Karri et al. 2018b; Li et al. 2018) However, we did notice that one subject with post-amputation PLP had carry-over effect for one month(Li et al. 2012a). We plan to screen these patients with long-lasting carry-over effects. These patients will be excluded from the subject should this happen.

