In Experiment 1, we plan to use our recent BreESTim and EStim protocols (Li et al. 2013; Li et al. 2014; Li et al. 2016) to measure mechanical sensation threshold, thermal (cold/warm detection, cold/hot pain) thresholds, and electrical sensation and pain thresholds in the treatment limb and contralateral limb. The same group of subjects will receive both BreESTim and EStim at a randomized yet balanced order with at least 7 days apart. The same amount of electrical stimulation (120 stimuli) will be given during both BreESTim and EStim. The purpose of this aim is to investigate whether BreESTim could have better analgesic effect than EStim in amputee subjects with chronic phantom limb pain as we observed in healthy subjects. We expect increased electrical pain thresholds in both limbs after BreESTim because of its central desensitization effects.

In Experiment 2, a group of subjects will receive BreESTim at two different doses (120 vs. 240 stimuli) on two different days with at least 7 days apart. The purpose is to compare the extent and duration of analgesic effects between two doses of BreESTim. We expect that BreESTim240 could have similar degree of pain reduction but with longer duration compared to BreESTim120, as shown in our pilot study. Therefore, we expect to use BreESTim240 in Experiment 3 for the long-term intervention.

[figure not shown]

Figure 7: Illustration of study design for Experiments 3

In Experiment 3, the same established protocol will be used (Li et al. 2012a; Li 2013). The effect of two interventions (BreESTim and EStim) will be compared. Each intervention consists of 240 stimuli/session (about 40-50 min/session), 1 session/day for 10 consecutive sessions (over 2 weeks). After a follow-up (wash-out) period of two weeks, the same subject will be treated with the other intervention with a same follow up of 2 weeks. The intensity of stimulation will be adjusted as subjects could tolerate. Electrical stimulation will be delivered to the median nerve on the dominant side. The wash-out/follow-up period of 2 weeks allows removal of accumulative or carry-over effect from the previous intervention.

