Experiment 2 The aim of this experiment is to explore this “dose-response” effect of BreESTim, by comparing the analgesic effects of two doses of single-session BreESTim. The same BreESTim protocol in Exp 1 will be used for Exp 2. In Exp 2, only BreESTim will be used. Two doses of BreESTim (120 vs. 240 electrical stimuli) will be given at least one week apart in a randomized order. Outcome measures, including VAS, QST thresholds, will be recorded pre- and 10 minutes post-intervention. Duration of analgesic effect (lasting hours) will also be recorded.

Experiment 3 The experimental set-up will be similar to Experiments 1&2. There are two different interventions – BreESTim and EStim. Each intervention consists of 240 stimuli/session (about 40-50 min/session), 1 session/day for 10 sessions (over 2 weeks, no treatment in the weekends). After a follow-up (wash-out) period of two weeks, the same subject will be treated with the other intervention with a same follow-up of 2 weeks. The intensity of stimulation will be increased gradually as patients could tolerate. Aversiveness of electrical stimulation is part of treatment strategy. During EStim, a single-pulse electrical stimulation is delivered to the forearm through surface electrodes randomly, while electrical stimulation is triggered by volitionally effortful inhalation during BreESTim as in Exp 1.

Specimens:

No specimens will be collected

5. Human Subjects

As mentioned above, we plan to recruit a total of 64 amputee subjects with phantom limb pain, including 16 subjects for Aim 1, 18 subjects for Aim 2, and 30 subjects for Aim 3. The number of subjects was estimated based on the pilot data.

• Subject recruitment/assignment

The collaborating physician (Co-I, [name]) will screen patients from the outpatient clinic of TIRR Memorial Hermann Hospital. We plan to register the project on www.clinicaltrials.gov. If patients are not currently seen by [name], but are willing to participate in the project, they need to see [name] for screening and monitoring. In addition, [name] will monitor medical conditions of the patients and manage medical problems as needed. Patients will be recruited and enrolled in the project if they meet the following criteria:

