Experiment 2 Similar to Exp 1, repeated-measures two-way ANOVA tests with factors INTERVENTION (2 levels, BreESTim 120 vs. 240) and TIME (pre- and post-intervention) will be tested on dependent variables, including VAS, QST thresholds (tactile, electrical, and thermal), to determine statistical significance between two interventions. Paired t-tests will be used to compare the duration of analgesic effect (lasting hours) between two interventions. p value is set at 0.05. As shown in the pilot data, we expect that BreESTim could have dose-dependent effects on the duration but not the degree of analgesic effects. These results also suggest that BreESTim could have cumulative effects if patients receive interventions repeatedly over a period of time.

In Experiment 3, Repeated-measures two-way ANOVA will be performed to determine statistical significance between two interventions. Factors include INTERVENTION (BreESTim vs. EStim) and TREATMENT (Pre- and Post-intervention, and Followup). Variables are VAS and modified VAS and QST parameters, GWB, and CES-D. It is hypothesized that the effect of pain reduction is greater in BreESTim than in EStim for amputation patients, manifested by pain reduction on VAS assessment and parallel change of increased electrical pain threshold as shown by pilot data in Experiments 3. Furthermore, pain reduction is accompanied by improvement in general well-being and mood.

Demographic data will be analyzed descriptively. Personal information will be de-identified. HSC-MS-20-1032

7. Potential Risks/Discomforts:

The risks associated with this study are minimal. Electrical stimulation has been used extensively in clinical settings. Patients may feel uncomfortable, or even painful during electrical stimulation. The patients will be specifically instructed that they are encouraged to increase the intensity of electrical stimulation to the level they may feel comfortable, but they need to be able to tolerate at that level if given repetitively. They are also explicitly instructed to decrease the intensity of electrical stimulation if they can not tolerate it. Surface electrodes can cause skin irritation from the tape adhesive or the electrode paste. Breathing through a face mask may be make patients feel uncomfortable. All tested subjects in the previous studies (approximately 100 subjects, including patients) tolerated the mask well.

8. Benefits:

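### Experiment 3 uses the same two weeks as follow-up and wash-out: if change from each course's own Pre is what is tested, BreESTim relief that outlasts the wash-out and then fades would overstate its advantage

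*Combined protocol and SAP*

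**What the plan says.** **Design.** Section 4.D (Experimental setup, Experiment 3): "After a follow-up (wash-out) period of two weeks, the same subject will be treated with the other intervention with a same follow-up of 2 weeks". Section 4.D (Experimental Design) gives the reasoning: "The wash-out/follow-up period of 2 weeks allows removal of accumulative or carry-over effect from the previous intervention".

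**Analysis.** Section 6, Experiment 3: "Factors include INTERVENTION (BreESTim vs. EStim) and TREATMENT (Pre- and Post-intervention, and Followup". The hypothesis reads: "It is hypothesized that the effect of pain reduction is greater in BreESTim than in EStim for amputation patients". The ANOVA term that tests it is not named. For Experiment 1, the power paragraph in Section 4.C uses the same kind of ANOVA to ask "whether any change in VAS score was due to the interaction between INTERVENTION and TIME".

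**Carry-over.** Section 4.D (Experimental Design) reports, from experience in spinal cord injury, "that an interval of 7 days is sufficient for subjects to return to their baseline after BreESTim treatment". It then adds: "we did notice that one subject with post-amputation PLP had carry-over effect for one month". Patients with long-lasting carry-over are to be screened for and excluded, but no criterion or time point is given. The same section expects the repeated BreESTim sessions to have a cumulative effect.

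**Not stated in the text.** The days on which the first Followup and the second Pre are measured. Figure 7, the Experiment 3 design, is not visible in the text available and may show them.

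**The concern.** Followup can show a BreESTim effect only if relief is still present in the two weeks after the course. The second Pre is a clean baseline only if that relief has gone. One interval is asked to do both jobs.

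In a patient given BreESTim first, residual relief counts for BreESTim at Followup. The same relief lowers the starting point of the EStim course. If it then wears off, pain seems to rise under EStim for reasons unrelated to EStim. Both movements favour BreESTim in a contrast of changes from own Pre. Aim 3 asks about the long-term effect, so this is the situation the experiment hopes to find, and nothing in the planned ANOVA would reveal it.

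**Working it through.** **The plan's own figure.** The documents give no figure for carry-over. The only Experiment 3 figure to reproduce is the sample size in Section 4.C. A crossover t-test with SD of differences 4.8 (√2 × 3.4 = 4.81), two-sided 0.05 and a difference of 3.0 gives 79.6% power at N = 22 and 83.3% at N = 24. So 24 is the smallest even N with at least 80%, and 24/0.8 = 30. Both stated figures reproduce. Separately, the same sentence gives means of 4.0 and 2.0, a difference of 2.0, for which N would be 48; that needs its own reconciliation.

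**Notation** (relief in VAS points, positive is good):
- b, e: relief at Post from BreESTim and EStim.
- rB, rE: residual relief at the end of the two weeks, taken as both Followup and second Pre.
- p, q: fraction of the first-course residual still present at the second Post and second Followup, added to the second course's own effect.

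None of these is given in the documents. Sequences are assumed equal in size.

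**Change from own Pre, BreESTim minus EStim**
- BreESTim first: Post (b − e) + (1 − p)rB; Followup (rB − rE) + (1 − q)rB.
- EStim first: Post (b − e) − (1 − p)rE; Followup (rB − rE) − (1 − q)rE.
- Average: Post (b − e) + (1 − p)(rB − rE)/2; Followup (rB − rE)[1 + (1 − q)/2].

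With p = q = 0, Followup is multiplied by 1.5 and Post gains (rB − rE)/2. With p = q = 1, or rB = rE, there is no bias.

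**Other contrasts from the same data**
- Raw levels: Post (b − e) − p(rB − rE)/2; Followup (rB − rE)(1 − q/2).
- INTERVENTION main effect over the three occasions: too small by (1 + p + q)(rB − rE)/6.

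**Example**, b = 3, e = 0, rB = 1, rE = 0 (truth: Post 3.0, Followup 1.0, main effect 4/3 = 1.33):

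| p, q | Own-Pre Post | Own-Pre Followup | Raw Post | Raw Followup | Main effect |
|---|---|---|---|---|---|
| 0, 0 | 3.50 | 1.50 | 3.00 | 1.00 | 1.17 |
| 0.5, 0.25 | 3.25 | 1.38 | 2.75 | 0.88 | 1.04 |
| 1, 1 | 3.00 | 1.00 | 2.50 | 0.50 | 0.83 |

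Simulation of the own-Pre contrasts (24 patients, 20,000 replicates) gave 3.50 and 1.51 for the first row and 3.00 and 0.99 for the last. With rB = 2 and p = q = 0, the own-Pre values are 4.0 and 3.0 against a truth of 3.0 and 2.0.

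**A smoother fading pattern.** Assume relief of 2.4 at Post (the pilot fall after the larger dose, 5.9 − 3.5), no EStim residual and constant proportional decay. The fraction kept per two weeks is f = rB/2.4, so p = f and q = f².
- Post excess = rB(1 − f)/2: 0.20, 0.29 and 0.17 for rB = 0.5, 1 and 2. The maximum is 0.30, at rB = 1.2.
- Followup at rB = 2: f = 0.833, f² = 0.694, so 2 × (1 + 0.306/2) = 2.31 against 2.0.

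On this pattern the bias is well below the ceilings.

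**The case against.** - **The contrast is not specified.** Section 6 names factors, not the tested term, and Section 4.C sizes Experiment 3 on a crossover t-test of VAS. A reader might infer that carry-over must flatter BreESTim. The text does not support that: raw levels are unbiased or pulled toward zero, and the main effect is attenuated. What stands is that pain reduction, together with the interaction used in Experiment 1, makes change from own Pre the natural reading.
- **Lasting relief is not the worst case.** A reader might infer that any lasting relief is counted twice. Relief that continues unchanged through the second course gives no bias in own-Pre contrasts. The bias needs relief present at the second Pre that later fades. The one-month case shows that relief can outlast two weeks, but Section 3 says pain returned at 28 days after an accidental stimulation, so natural fading is not shown.
- **A shared reading is an inference.** It is tempting to say that one measurement fills both cells, which would raise the noise variance of the Followup contrast from 4 to 6 units (√1.5 = 1.22, so the standard error rises 22%). Only the interval is shared in the text. Section 4.D records VAS immediately before each intervention in Experiment 1 and calls the Experiment 3 set-up similar, which favours a separate second Pre. If Followup falls earlier, when relief is larger, its inflation is below 50%.
- **The plan does address carry-over.** Excluding patients with long-lasting carry-over would shrink the residual. But the rule has no criterion and, if applied after the first course, removes patients because of their response to treatment and truncates the effect Aim 3 seeks.
- **The size is unknown.** Pilot relief followed single sessions and lasted hours (14.5 to 26.1 after BreESTim in Experiment 2). The documents do not say how many patients would keep relief for two weeks.

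**Conclusion.** The point holds conditionally. The shared interval and the absence of period, sequence and carry-over terms are in the text. If change from own Pre is tested, and BreESTim leaves more residual relief than EStim which then fades, the contrast overstates BreESTim by at most 50% at Followup and by at most half the difference in residual relief at Post. These ceilings assume balanced sequences and Followup at the end of the interval. If every patient had BreESTim first and EStim left no residual, the excess would double.

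The bias is zero if residuals are zero or equal, or if relief persists unchanged. The documents do not establish that a residual exists, how large it is, or that the result will be inflated. A reader might also conclude that the first Pre must replace the second as sole baseline. That does not follow: it leaves raw levels, which understate the Post advantage by p(rB − rE)/2 against an overstatement of (1 − p)(rB − rE)/2 for own-Pre, and so do worse when p exceeds 0.5. This is a low-cost improvement that protects the Aim 3 conclusion, not a defect that invalidates the experiment.

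**What to change.** In Section 6, Experiment 3:
- Name the tested contrast, and state the days of the first Followup and second Pre.
- Add period and sequence terms. These are standard for the crossover but do not remove unequal carry-over: the averages above already weight the two sequences equally.
- Report second-course minus first-course Pre by sequence, with a confidence interval.
- Prespecify, as a sensitivity analysis, a first-course-only comparison of the randomised sequences at Post and Followup, adjusted for the first Pre. No earlier course can affect it.
- Optionally show Post and Followup levels without subtracting the second Pre, labelled conservative.

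In Section 4.D, reconcile the statement that two weeks removes carry-over with the one-month case and the exclusion plan, and state that plan's criterion and timing. No wash-out length is proposed here.

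Cost: wording only, using measurements already planned. The first-course comparison is between patients (12 per sequence if 24 complete and sequences are equal) and so less precise; the between-patient SD needed to say by how much is not given. The reported advantage may be smaller. The choice should be made before the data are analysed, since changing the contrast afterwards would be post hoc.

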It is expected that electrical pain threshold will be further increased after BreESTim with parallel reduction in pain perception, while there is no or minimum change after EStim and no significant change in pain perception. Pain threshold will be measured using QST. Pain perception will be characterized by duration and amount of change in pain on visual analog scale (VAS), i.e., how much pain is reduced and how long it lasts. As such the effect of treatment is quantified by reduction x hours.

The secondary outcome measurement will be General Well-Being (GWB) Schedule Survey and Center for Epidemiologic Studies Depression Scale (CES-D), NIMH Survey to examine the possible effect of pain reduction on general well-being, depression and quality of life of the patients. These surveys have been well validated and commonly used (Sherman et al. 1984; Wartan et al. 1997; Kooijman et al. 2000).

The long-term BreESTim treatment is expected to have some cumulative analgesic effects. However, we decide to keep the same regime of medications, because change in medications will be a confounding factor. Therefore, the subjects will be explicitly instructed to maintain the same dose and frequency of pain medications after the BreESTim treatment even if pain is improved. The collaborating investigator [name] will screen and monitor their medications. This is exploratory at this time. If the baseline pain level improves after the 2-week BreESTim treatment, a clinical trial is warranted. Change in pain medications may be explored further in the future studies.

- **Experimental setup (BreESTim and EStim protocols and measurement)**

Experiment 1 We plan to use our recent BreESTim and EStim protocols (Li et al. 2013; Li et al. 2014). Briefly, subjects will be seated comfortably with the arm on the experimental table (Fig 8). Subjects will wear a facemask that will be connected to a Pneumotach system to record breathing signals and to prevent hyperventilation. Surface electrodes will be trimmed to be applied to the median nerve ipsilateral to the affected side proximal to the wrist line (see Fig 8). Note that important acupuncture points (Neiguang and Waiguan) are located beneath the electrodes. So these points will be stimulated during both BreESTim and EStim).

[figure not shown]

Figure 8 Experimental settings. On the right panel, an electrical stimulus (Lower) is triggered when the airflow rate (Upper) of a forceful inhalation reaches 40% of its maximum value.

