Two interventions (BreESTim vs. EStim) will be given to the same subject on a different day with at least 7 days apart. As in previous studies(Li et al. 2013; Li et al. 2014), a total of 120 electrical stimuli will be delivered for each intervention. The order of interventions will be randomized and balanced across subjects. Both interventions will be given at the same time of the day, as determined by subject's schedule. It is important to emphasize that subjects will be explicitly instructed to maintain the same pain regime even they feel that treatment has helped in pain reduction, such that pain reduction is mainly related to BreESTim or EStim.

Outcome measurement includes visual analogue scale (VAS) and Quantitative Sensory Testing (QST) and Hear rate variability (HRV). The VAS method has been extensively used and validated (McCarthy et al. 2005). Using VAS to rate pain intensity has been considered a standardized measurement to evaluate effectiveness of deep brain stimulation for pain management in a multi-center study by Medtronic (Medtronic, Minneapolis, MN). These results have been reported to US Food and Drug Administration for judgment on the efficacy of pain management(Coffey 2001). In the project, we plan to use a modified VAS to quantify pain reduction. As used in our pilot study (Li et al. 2012a; Li 2013), the effect of pain reduction is characterized by duration and amount of change in pain on VAS, i.e., how much pain is reduced and how long it lasts. As such the effect of treatment is quantified by reduction×hours. The effect and the intensity of stimulation will be recorded daily during the course of treatment. For VAS, the duration of analgesic effect from the intervention will also be recorded. VAS scores will be obtained before and 10 minutes after. Post-intervention VAS will be also assessed through follow-up phone calls every 4 hours except night time (10pm – 7am). It is important to emphasize that subjects will be explicitly instructed to maintain the same pain medication regimen even if they feel that treatment have helped in pain reduction.

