Inclusion criteria: A patient who 1) has neuropathic PLP after amputation of one limb, upper or lower limb; NOTE that BreESTim has been shown to be effective for neuropathic pain management in patients after traumatic and non-traumatic spinal cord injury in recent studies(Li et al. 2016; Li et al. 2018). Therefore, we plan to recruit patients with chronic neuropathic PLP from both traumatic and non-traumatic limb amputation. 2) has chronic pain, >3 months; 3) is between 18 to 75 years of age; 4) is stable on oral pain medications at least two weeks. Patients are instructed to continue their pain medications as prescribed during the intervention period.

Exclusion criteria: Patients will be excluded if they 1) are currently adjusting oral pain medications for their neuropathic pain; 2) have pain, but not neuropathic, e.g., from inflammation at the incision wound of the residual limb; 3) have a pacemaker to avoid possible side effect of electrical stimulation; 4) have amputation in multiple limbs; 5) are not able to follow commands, or to give consent; 6) have asthma or other pulmonary disease; 7) are not medically stable.

Gender will be balanced

Potential subject populations and recruitment: Subjects will be recruited from TIRR outpatient clinic.

6. Data Collection and Analysis

Data collection details have been described above. Data analysis is described here.

Experiment 1 Repeated-measures two-way ANOVA tests with factors INTERVENTION (2 levels, BreESTim and EStim) and TIME (pre- and post-intervention) will be tested on dependent variables, including VAS, QST thresholds (tactile, electrical, and thermal), to determine statistical significance between two interventions. Paired t-tests will be used to compare the duration of lasting hours between two interventions. p value is set at 0.05. As observed in the pilot data, we expect that BreESTim could have central desensitization and analgesic effects on patients with phantom limb pain, but no such effect after EStim. These findings would suggest that the central desensitization effect of BreESTim could be translated to analgesic effects in patients with PLP. Furthermore, the findings of analgesic effects along with desensitization effects in patients with PLP support central sensitization as a plausible mechanism that mediates post-traumatic PLP.

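### Experiment 3 enters modified VAS (reduction x hours), itself a change measure, in a Pre/Post/Followup ANOVA where its Pre level carries no information

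*Combined protocol and SAP*

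**What the plan says.** Section 6 (Data Collection and Analysis), Experiment 3, gives a single analysis, a repeated-measures two-way ANOVA: "Factors include INTERVENTION (BreESTim vs. EStim) and TREATMENT (Pre- and Post-intervention, and Followup"). The dependent variables follow in one list: "Variables are VAS and modified VAS and QST parameters, GWB, and CES-D".

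The measure is described in section 4, part D. The outcome text under Experiment 1 introduces it: "In the project, we plan to use a modified VAS to quantify pain reduction". It is characterised there by how far VAS changes and for how long. The Experiment 3 design text says "As such the effect of treatment is quantified by reduction x hours".

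Hours of relief, one component of the measure, have their own test in the other two experiments. Experiment 1: "Paired t-tests will be used to compare the duration of lasting hours between two interventions". Experiment 2: "Paired t-tests will be used to compare the duration of analgesic effect (lasting hours) between two interventions". Experiment 3 has no matching sentence. Its sample size (section 4, part C) rests on a 2 x 2 crossover t-test of plain VAS.

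**The concern.** A Pre/Post/Followup factor suits a variable that can be measured at each of the three times. VAS, QST, GWB and CES-D can. Modified VAS is already a change: before treatment there is no reduction and no duration, so Pre is either the same constant for everyone or missing. The analyst must enter a constant or drop the level, and the text does not say which. A Followup value also has to come from somewhere.

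At stake is the test of the quantity by which the protocol expresses the Experiment 3 treatment effect. A constant Pre can break sphericity and so inflate the interaction test. It also means the main effect averages over an empty level and a Followup level of unknown meaning.

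**Working it through.** **The plan's own figure.** Section 4.C gives a difference of 3.0, an SD of differences of 4.8 and N = 24. The standardised effect is 3.0/4.8 = 0.625. A crossover t-test with 22 df has 83.3% power at N = 24, which is the smallest even N reaching 80%. Allowing 20% dropout, 24/0.8 = 30. Both stated numbers reproduce. They concern plain VAS and are borrowed below only as an illustrative effect and sample size. The same paragraph gives group means of 4.0 and 2.0, which differ by 2.0; that is a separate matter.

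**Set-up.** Let D be a patient's between-intervention difference at (Pre, Post, Followup). With Pre entered as zero, D = (0, X, Y). Scale X to SD 1, let Y have SD r, and let their correlation be ρ. Assumptions: normal data, n = 24, r of 0, 0.5 or 1, and ρ from 0 to 0.8. None of these values is in the documents.

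**False positives, Followup also zero (Y = 0).**
- Interaction mean square: n·x̄²·(2/3)/2 = n·x̄²/3.
- Error mean square: (2/3)·(n−1)s²/[2(n−1)] = s²/3.
- Hence F = n·x̄²/s² = t², a one-degree-of-freedom statistic with 23 error df. Its correct 5% limit is F(1,23) = 4.28, but the uncorrected table uses F(2,46) = 3.20.
- P(t² > 3.20 on 23 df) = 8.7%.

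**False positives, Followup varying.** Sphericity needs equal variances of Post−Pre, Followup−Pre and Post−Followup, which are 1, r² and 1 + r² − 2ρr. At r = 1, ρ = 0.5 they are 1, 1, 1, so it holds. At r = 0.5, ρ = 0.5 they are 1, 0.25, 0.75, so it fails. Simulated rates at nominal 5%:

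| Followup SD relative to Post SD | Interaction, uncorrected |
|---|---|
| 0 | 8.7% |
| 0.5 | about 6.6% to 7.4% |
| 1 | about 5% to 6% |

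Across these settings the Greenhouse-Geisser interaction rejects about 4.4% to 5.1% of the time, and the INTERVENTION main effect about 5%.

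**Power, effect of 0.625 at Post only.** The main effect tests the mean of (0, X, Y), so its noncentrality is √24 × 0.625/√(1 + r² + 2ρr) = 3.06/√(1 + r² + 2ρr), on 23 df.

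| r | ρ | √(1 + r² + 2ρr) | Noncentrality | Power |
|---|---|---|---|---|
| 0 | any | 1.00 | 3.06 | 83% |
| 0.5 | 0 | 1.12 | 2.74 | 75% |
| 0.5 | 0.8 | 1.43 | 2.14 | 54% |
| 1 | 0 | 1.41 | 2.17 | 55% |
| 1 | 0.5 | 1.73 | 1.77 | 40% |
| 1 | 0.8 | 1.90 | 1.61 | 34% |

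A paired t-test on Post has noncentrality 3.06 and about 83% power in every row.

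**Power, effect persisting at Followup.** If Followup has the same standardised effect, the noncentrality is multiplied by (1 + r). Because (1 + r)² ≥ 1 + r² + 2ρr, the main effect then loses nothing. At r = 1, ρ = 0.5 its power is 92%.

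**Other text that might settle it.** Under Experiment 1, "The effect and the intensity of stimulation will be recorded daily during the course of treatment"; for Experiment 3, "The experimental set-up will be similar to Experiments 1&2". If daily recording carries over, each intervention yields up to 10 values, and the available text does not map them to Post or Followup.

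**The case against.** The strongest reply is that most of the harm is avoidable within the planned model. The inflation appears only when sphericity fails and no correction is made, and the plan does not exclude one. With both Pre and Followup at zero, the INTERVENTION main effect is algebraically the paired t-test on Post. Dropping Pre leaves a two-level factor with no sphericity problem. The power loss concerns the main effect and an effect confined to Post. In that scenario, with equal SDs and correlation 0.5, the Greenhouse-Geisser interaction has about 87% power, and section 4.C names the interaction as the effect of interest for Experiment 1. All of this stands, and it limits the severity. It does not give the Pre level any content or supply a Followup value, and the answer still depends on which effect is read.

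A second reply is that the missing rule may be written down. Some text just before the Experiment 3 power analysis, and Figure 7 showing the Experiment 3 design, are not in the available copy. A reader might infer that the Pre and Followup values will be chosen after the data are seen. The documents do not support saying so; one can say only that no available text fixes them.

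A third is that the reference VAS is never named. That too is right. The pre-intervention reference is inferred from the wording about change and from VAS being taken before and 10 minutes after treatment.

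**Conclusion.** The point holds as a mismatch between one variable and its model, and its impact is minor. The uncorrected interaction error of up to 8.7% assumes Pre entered as zero, normal data and N = 24; it is close to nominal with a Greenhouse-Geisser correction. Main-effect power of about 34% to 75%, against about 83%, further assumes an effect at Post only and a Followup value that varies.

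A reader might go further and conclude that Experiment 3's error rate or its main pain conclusion is compromised. The documents do not support that. Modified VAS is not named primary, the hypothesis is expressed through VAS and electrical pain threshold, power is set on plain VAS, and VAS, QST, GWB and CES-D fit the three-level factor.

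**What to change.** Remove modified VAS from the Pre/Post/Followup ANOVA and leave VAS, QST, GWB and CES-D in it. Derive one reduction x hours value per patient per intervention by a rule fixed in advance, and compare BreESTim with EStim on that value by one prespecified paired crossover contrast. This agrees with the paired t-tests for hours of relief in Experiments 1 and 2 and with the 2 x 2 crossover basis of the Experiment 3 sample size. Period adjustment is optional.

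The cost is a few sentences of wording, with no change to sample size or treatment. The one loss is that a single summary value no longer tests Post and Followup separately for this measure.
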